7.1.7 Laboratory Test Abnormalities

Local laboratories will be used for all laboratory tests. Laboratory test abnormalities will be recorded on the AEs pages of the eCRF.

Any laboratory result abnormality fulfilling the criteria for an SAE should be reported as such, in addition to being recorded as an AE in the eCRF.

Any treatment-emergent abnormal laboratory result which is clinically significant, i.e., meeting one or more of the following conditions, should be recorded as a single diagnosis on the AE page in the eCRF:

- Accompanied by clinical symptoms
- Leading to a change in study medication (e.g., dose modification, interruption, or permanent discontinuation)
- Requiring a change in concomitant therapy (e.g., addition of, interruption of, discontinuation of, or any other change in a concomitant medication, therapy, or treatment)

7.1.8 Follow-up of Abnormal Laboratory Test Values

In the event of medically significant unexplained abnormal laboratory test values, the tests should be repeated and followed up until they have returned to the normal range and/or an adequate explanation of the abnormality is found. If a clear explanation is established it should be recorded on the eCRF.

7.2 HANDLING OF SAFETY PARAMETERS

7.2.1 Recording and Collection of Adverse Events

Information about all AEs, whether volunteered by the patient, discovered by Investigator questioning, or detected through physical examination, laboratory test, or other means, will be collected on the Adverse Event eCRF page, documented in the patient's medical records, and followed as appropriate.

All AEs and SAEs, regardless of the relationship to the trial drug, will be recorded in the eCRF.

All AE reports should contain a brief description of the event, date and time of onset, date and time of resolution, intensity, treatment required, relationship to trial drug, action taken with the trial drug, outcome, and whether the AE is classified as serious.

All AEs experienced after the patient has started study treatment must be recorded on the AE form of the eCRF, as well as all new AEs experienced during the study and during further five Safety Follow-Up Visits 1 month, 3 months, 6 months, 9 months, and 12 months after the last dose of study treatment (± 5 days). SAEs considered related to study drug are to be reported indefinitely.

A pre-existing medical condition that is present at the start of the study should be recorded on the Medical History eCRF.

Worsening and/or progression of advanced BCC should not be recorded as an AE or SAE. These data will be captured as efficacy assessment data only.

If a female patient becomes pregnant while receiving investigational therapy or within 9 months *or within the designated window per approved local prescribing information for vismodegib (where available), whichever is longer*, after the last dose of investigational product, the Investigator should report to the Sponsor immediately within one working day (24 hours) of learning of the pregnancy.

Abortion, whether therapeutic or spontaneous, should always be classified as serious (as the Sponsor considers these medically significant), recorded on the eCRF, and expeditiously reported to the Sponsor.

7.2.2 Reporting of Serious Adverse Events (Immediately Reportable)

Any clinical AE or abnormal laboratory test value that is *serious* and which occurs during the course of the study (as defined in Section 7.1.1.3 above), must be reported to Roche **within 24 hours** of the Investigator becoming aware of the event (expedited reporting).

The following proviso applies:

- **During the Screening Period, after written informed consent has been signed only SAEs related to protocol procedures will be reported.**
- **From the first administration of vismodegib, all SAEs must be reported.**

Related SAEs **MUST** be collected and reported regardless of the time elapsed from the last study drug administration, even if the study has been closed. Suspected Unexpected Serious Adverse Reactions (SUSARs) are reported to Investigators at each site and associated Institutional Review Board/Independent Ethics Committee (IRB/IEC) when the following conditions occur:

- The event must be a SAE
- There must be a certain degree of probability that the event is an adverse reaction from the administered drug
- The adverse reaction must be unexpected, that is to say, not foreseen in the Investigator's Brochure (for an unauthorized medicinal product)

When all patients at a particular site are off treatment as defined by the protocol:

- Only individual SUSAR reports originating in that particular trial will be forwarded to the site and associated IRB/IEC on an expedited basis
- Individual SUSARs considered to be a significant safety issue and/or which result in Roche recommending a change to the ICF, will be reported in an expedited manner to all Investigators and IRBs/IECs
- SUSAR reports originating from other trials using the same IMP will be provided as 6-monthly SUSAR Reports to Investigators and IRBs/IECs where long-term follow-up studies are carried out, unless they are considered significant

Unrelated SAEs must be collected and reported during the study and for up to 12 months after the last dose of study medication.

This study adheres to the definition and reporting requirements of **ICH Guideline for Clinical Safety Data Management, Definitions and Standards for Expedited Reporting, Topic E2**. Complete information can be found in [Appendix 4](#).

7.2.3 Reporting of Non-Serious Events of Special Interest

Not applicable.

7.2.4 PRO Data and Adverse Event Reporting

Adverse event reports will not be derived from PRO data. However, if any patient responses suggestive of a possible adverse event are identified during site review of the PRO questionnaires, site staff will alert the investigator, who will determine if the criteria for an adverse event have been met and will document the outcome of this assessment in the patient's medical record per site practice. If the event meets the criteria for an adverse event, it will be reported on the Adverse Event eCRF.

7.3 WARNINGS AND PRECAUTIONS

No evidence available at the time of the approval of this study protocol indicated that special warnings or precautions were appropriate, other than those noted in the Investigators' Brochure.

8. STATISTICAL CONSIDERATIONS AND ANALYTICAL PLAN

8.1 PRIMARY AND SECONDARY VARIABLES

The final analysis for safety and efficacy will be performed when the last patient on treatment develops progressive disease (as determined by the Investigator) or unacceptable toxicity, withdraws consent, or dies; the treating physician deems the patient is no longer benefitting from treatment; or the study is terminated by the Sponsor, or 12 months after the last dose of vismodegib in the last enrolled patient still on study, whichever occurs first.

Additional interim analyses will be performed as described in Section [8.2.1.2](#).

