Study enrollment is planned to end in the EU if vismodegib becomes commercially available after regulatory approval for the treatment of locally advanced or metastatic BCC. Study enrollment is planned to end successively in non-EU countries participating in this study if vismodegib becomes commercially available after regulatory approval for the treatment of locally advanced or metastatic BCC in the respective country. However, patients already enrolled in this study and who are still benefitting from vismodegib in the opinion of the Investigator will continue to receive vismodegib as a study medication until the development of progressive disease (as determined by the Investigator), unacceptable toxicity, consent withdrawal, death, reasons deemed by the treating physician, or study

termination by the Sponsor.

The study will end when the last patient on treatment develops progressive disease (as determined by the Investigator) or unacceptable toxicity, withdraws consent, or dies; the treating physician deems the patient is no longer benefitting from treatment and has completed the safety follow up visits, or the study is terminated by the Sponsor, or 12 months after the last dose of vismodegib in the last enrolled patient still on study, whichever occurs first.

The Sponsor reserves the right to end study enrollment at any time. If study enrollment is stopped prior to commercial availability of vismodegib, patients already enrolled will be informed of the reason for discontinuation of study enrollment and, in the absence of a significant product safety concern or other circumstances, will be allowed to continue vismodegib until disease progression, unmanageable toxicity, withdrawal of consent, reasons deemed by the treating physician, or death of the patient, whichever occurs first.

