It is anticipated that approximately 1200 patients will be enrolled over approximately 3.5 years. The study will end when the last patient enrolled in this study develops Progressive Disease (PD) (as determined by the Investigator), unacceptable toxicity, withdraws consent, dies, or the treating physician deems that patient is no longer benefitting from treatment or the study is terminated by the Sponsor, or 12 months after the last dose of vismodegib in the last enrolled patient still on study, whichever occurs first.

The Sponsor reserves the right to end enrollment at any time. If study enrollment is discontinued prior to commercial availability of vismodegib, patients already enrolled will be informed of the reason for discontinuation of study enrollment and, in the absence of a significant product safety concern or other circumstances, will be allowed to continue vismodegib until disease progression, unmanageable toxicity, withdrawal of consent, reasons deemed by the treating physician or death of the patient, whichever occurs first.

Treatment scheme:

Screening	Study Treatment Phase	Safety Follow-Up
Day –28 to –1	Continuous once-daily oral dosing of vismodegib at a dosage of 150 mg per administration once-daily until one of the following occurs: disease progression, intolerable toxicity most probably attributable to vismodegib, consent withdrawal, death, study termination by the Sponsor, or other reason deemed by Investigator	Five Safety Follow-Up Visits 1 month, 3 months, 6 months, 9 months, and 12 months after the last dose of vismodegib (±5 days)

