3.1.6 End of Study

Study enrollment will end in the EU if vismodegib becomes commercially available after regulatory approval for the treatment of locally advanced or metastatic BCC. Study enrollment will end successively in non-EU countries participating in this study if vismodegib becomes commercially available after regulatory approval for the treatment of locally advanced or metastatic BCC in the respective country. However, patients already enrolled in this study and who are still benefitting from vismodegib in the opinion of the Investigator will continue to receive vismodegib until the development of progressive disease (as determined by the Investigator), unacceptable toxicity, consent withdrawal, death, reasons deemed by the treating physician, or study termination by the Sponsor.

It is anticipated that approximately 1200 patients will be enrolled over approximately 3.5 years. Once the enrollment of 1200 patients is completed, an assessment of how many patients with metastatic BCC were enrolled under Protocol Amendment Version 4 (dated 8 May 2013) will be made. At that time, enrollment may be extended for up to 15 additional metastatic BCC patients in order to ensure adequate collection of data regarding the effect of vismodegib in metastatic BCC patients, as per Protocol Amendment Version 4 (dated 8 May 2013). The study will end when the last patient on treatment develops progressive disease (as determined by the Investigator), unacceptable toxicity, withdraws consent, or dies; the treating physician deems that the patient is no longer benefitting from treatment; or the study is terminated by the Sponsor, or 12 months after the last dose of vismodegib in the last enrolled patient still on study, whichever occurs first.

The Sponsor reserves the right to end study enrollment at any time. If study enrollment is stopped prior to commercial availability of vismodegib, patients already enrolled will be informed of the reason for discontinuation of study enrollment and, in the absence of a significant product safety concern, will be allowed to continue on vismodegib until disease progression, unmanageable toxicity, withdrawal of consent, reasons deemed by the treating physician, or death of the patient, whichever occurs first.

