5. SCHEDULE OF ASSESSMENTS AND PROCEDURES

All scheduled study assessments are outlined in [Table 1](#) (Schedule of Assessments).

All Screening/Baseline assessments, as outlined in [Table 1](#), must be performed within 28 days prior to the first administration of vismodegib on Day 1, Cycle 1. Results of tests or examinations performed as standard of care before obtaining informed consent and within the 28 days prior to commencing vismodegib may be used. Tumor assessment by physical examination should be performed within a maximum of 7 days prior to the first dose of study drug (baseline reading). If tumor assessment requires imaging, baseline CT/MRI scans should be performed within a maximum of 28 days prior to the first dose of study drug (on Cycle 1, Day 1). Non-measurable disease should be assessed within 28 days prior to study initiation.

All assessments during the Treatment Phase must be performed within a window ± 3 days, from Cycle 2 onwards of the day indicated on the schedule of assessment, with the exception of tumor assessments. The majority of the patients in this study have locally advanced BCC and in this disease setting measurable tumors are accessible to evaluation by physical examination every 4 to 8 weeks (± 5 days). If assessment requires imaging, CT and/or MRI scans should occur every 8 to 16 weeks (± 5 days) or as per institutional standards.

Eligibility for the study will be determined by the Investigator from the mandatory Screening/Baseline assessments performed during screening and according to the study inclusion/exclusion criteria. First dosing of vismodegib will be determined by the patient's eligibility and the laboratory assessments on Day 1 prior to dosing.

The treatment period will begin on Day 1, and patients will be followed until Investigator-assessed disease progression, unacceptable toxicities most probably attributable to vismodegib, patient consent withdrawal, death, reasons deemed by the treating physician, or study termination by the Sponsor. In addition, five Safety Follow-Up Visits 1 month, 3 months, 6 months, 9 months, and 12 months will occur after the last dose of vismodegib (± 5 days), as provided by this phase II safety study protocol. The first anti-cancer therapy received by the patient after discontinuation of study drug will also be recorded.

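### For every listed stopping reason, the study-end and final-analysis trigger fires before the 12-month safety follow-up that the protocol requires, and the sections disagree on whose event counts

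*Protocol*

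**What the plan says.** Final analysis. Protocol Section 8.1 states: "The final analysis for safety and efficacy will be performed when the last patient on treatment develops progressive disease". It then lists unacceptable toxicity, withdrawal of consent, death, the physician's judgement of no further benefit, Sponsor termination, and finally "12 months after the last dose of vismodegib in the last enrolled patient still on study, whichever occurs first". The Statistical Analyses part of the Synopsis has the same sentence.

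Study end. Section 3.1.6 uses the same list and the same earliest-event rule: "The study will end when the last patient on treatment develops progressive disease (as determined by the Investigator), unacceptable toxicity, withdraws consent, or dies". Section 3.1 has a parallel list but a different patient: "The study will end when the last patient enrolled in this study develops Progressive Disease (PD". The End of Study part of the Synopsis follows Section 3.1.6, except that one limb reads "the treating physician deems the patient is no longer benefitting from treatment and has completed the safety follow up visits".

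Follow-up required elsewhere. Protocol Section 5 says that "five Safety Follow-Up Visits 1 month, 3 months, 6 months, 9 months, and 12 months will occur after the last dose of vismodegib". Section 7.2.2 says: "Unrelated SAEs must be collected and reported during the study and for up to 12 months after the last dose of study medication". The SAP (Disposition) counts a patient as having completed the study after 12 months of follow-up if enrolled under protocol version 3 or later, and after 1 month under versions 1 or 2.

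**The concern.** A trigger that takes the earliest of a stopping event and a date 12 months after the last dose will normally take the stopping event. Follow-up to 12 months is mandatory and safety is the primary objective, yet nothing in Sections 3.1, 3.1.6 or 8.1 holds the study open or delays the analysis until that follow-up is done.

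The outputs exposed are those that need post-treatment time. They are the SAP tables and listings of adverse events still ongoing after discontinuation, which use 12-month completers or exclude patients who stopped within 6 months of the cut, and the capture of late serious adverse events and deaths.

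The second problem is that the last patient enrolled and the last patient on treatment are usually different people with different dates. The protocol therefore gives two study-end rules.

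**Working it through.** **1. The five statements side by side.** All five take the earliest limb.

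| Place (Protocol) | Governs | Patient named | Follow-up condition |
|---|---|---|---|
| Synopsis, Statistical Analyses | Final analysis | Last on treatment | None |
| Section 8.1 | Final analysis | Last on treatment | None |
| Synopsis, End of Study | Study end | Last on treatment | Completed visits, on the no-further-benefit limb only |
| Section 3.1 | Study end | Last enrolled | None |
| Section 3.1.6 | Study end | Last on treatment | None |

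**2. When the trigger fires.** Put the last remaining patient's last dose at month 0 and let E be the month of the stopping event. The trigger is T = min(E, 0 + 12).

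- Toxicity, withdrawal of consent, death on treatment, no further benefit, Sponsor termination: E = 0, so T = 0. None of the 12 follow-up months is guaranteed. The Synopsis wording changes this only for study end on the no-further-benefit limb.
- Progression: E is at or before 0. Section 6.1 lets treatment continue after progression following consultation with the medical monitor, so this limb can fire while dosing continues.
- A stop outside the list: no event limb fires and T = 12. The SAP's discontinuation listing shows such a case, a patient who asked to stop the drug but agreed to stay in follow-up. Section 4.5 recognises similar routes.

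This takes the last enrolled patient still on study to mean the last remaining patient. If it means the most recently enrolled patient, the 12-month clause in Section 8.1 would not be redundant. It could fire even earlier, while other patients are still on treatment.

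**3. Size under the on-treatment wording.** The plan states no figure, so this is an illustration.

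Inputs:
- N = 1215 (safety population in the SAP's Summary of Deaths).
- Uniform entry over 42 months (the protocol's 3.5 years).
- Exponential treatment duration, which is an assumption. The median m is 9.7 months (locally advanced cohort of the earlier pivotal study, Section 1.1.2.2) up to 20 months, an assumed upper value.

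For exponential durations, once enrolment has closed, the expected number of patients whose stop falls within 12 months of the last stop, counting the last patient, is 2^(12/m).

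- m = 9.7: 2^(1.237) = 2.36. Simulation gives 2.4, 95% range 1 to 7.
- m = 20: 2^(0.6) = 1.52. Simulation gives 1.5, 95% range 1 to 4.

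As a share of 1215 this is 2.36/1215 = 0.19% and 1.52/1215 = 0.12%.

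**4. Size under the last-enrolled wording.** With λ = ln 2/m, the expected number on treatment when enrolment closes is N(1 − e^(−42λ))/(42λ).

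- m = 9.7: 42λ = 3.001, giving 1215 × 0.950/3.001 ≈ 385.
- m = 20: 42λ = 1.456, giving 1215 × 0.767/1.456 ≈ 640.

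Under the exponential assumption the last-enrolled patient is equally likely to stop at any place in that queue, so on average about half are still on treatment at the trigger: 385/2 ≈ 192 and 640/2 = 320. Simulation gives about 196 and 319, with wide 95% ranges (9 to 379 and 15 to 630). On average a further 221 and 155 patients would have stopped less than 12 months before.

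**The case against.** The best defence is that the intent is plain. Five visits, 12-month collection of serious adverse events, the SAP's completion rule and the Synopsis's study-end text all point to 12 months. The data-cut rule itself sits in a separate specification to which the SAP refers (Data Cut Derivation), so a trigger sentence is not necessarily the data cut. No hypothesis is tested, and the SAP already restricts its persisting-event outputs to patients with enough follow-up. Much of this stands and limits the consequences. It does not reconcile the rules: a reader of Section 8.1 or 3.1.6 alone would close before the required follow-up.

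Four stronger readings are tempting, and the documents do not support them.

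- That the 12-month clause can never operate. It does operate for stops outside the list.
- That the primary safety tables lose months of events. The SAP (General AE Reporting) limits adverse event summaries, unless otherwise specified, to events starting within 30 days of the last dose, so new events at months 3 to 12 do not enter them. What remains is that, for the last patient, a trigger at month 0 does not cover even those 30 days.
- That the post-treatment pharmacokinetic aim is at risk. The amendment rationale at the front of the protocol says the population model has already been finalised with data to 12 months after treatment.
- That the patients cut short are the longest exposed. Nothing in the documents shows this.

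**Conclusion.** The point holds as a contradiction between stated rules. For every listed stopping reason, the final-analysis trigger (Synopsis, Section 8.1) and the study-end trigger (Sections 3.1 and 3.1.6) fire no later than the stopping event and do not wait for the follow-up required by Sections 5 and 7.2.2 and assumed in the SAP's completion rule. The Synopsis repairs one limb of one statement. The final cut can also move by up to 12 months according to one patient's recorded reason for stopping.

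Under the on-treatment wording the practical loss is small, about 2 patients of 1215, and falls mainly on the adverse-event resolution outputs and on late serious events and deaths. Under Section 3.1 as written it could be large, with an average of roughly 195 to 320 patients still on treatment. Both sizes rest on the assumed entry pattern and exponential durations. They show the scale of the ambiguity and do not predict conduct. Sponsor termination with many patients on treatment would truncate follow-up under any wording.

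**What to change.** Use one sentence in both places in the Synopsis and in Sections 3.1, 3.1.6 and 8.1: study end and final analysis occur when the last patient on treatment has completed the 12-month Safety Follow-Up Visit (or has died, withdrawn or been lost to follow-up earlier), or at Sponsor termination. Remove the earliest-event rule between the stopping event and the 12-month clause. Make clear that an early death or withdrawal of that patient does not close follow-up for others who stopped in the preceding 12 months.

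This is a change of wording and alters no treatment rule. The downside is a database lock up to 12 months later than the literal text allows, which matches visits already mandated. It does not protect follow-up if the Sponsor terminates the study.
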